### 4.7 Other Analyses

Not applicable.

### 4.8 Exploratory Analyses

Exploratory analyses may be conducted as appropriate. Any exploratory analyses that are performed will be appropriate titled and labeled as exploratory and will be clearly distinguished from planned analyses when results are reported in the Clinical Study Report.

## 5 INTERIM ANALYSES

Not applicable.

## 6 CHANGES IN THE PLANNED ANALYSES

Major changes of planned analysis from SAP version 1.0 are listed in the revision history.

## 7 DEFINITIONS AND CONVENTIONS FOR DATA HANDLING

The data will be handled as follows. The sponsor will determine how to handle all data prior to data base lock.

### Baseline Assessment

Unless otherwise specified, the baseline measurement is the last observed measurement among all available measurements, including from unscheduled assessments, prior to the first dose of randomized study drug for a given assessment.

### Change from Baseline, Percent Change from Baseline

Change from baseline will be defined as: Post-baseline value - Baseline value

% change from baseline will be defined as: (Change from baseline / Baseline value) \* 100

For efficacy analysis, % reduction from baseline will be calculated as: {(Baseline value – post-baseline value) / Baseline value} \*100.

### Visit Window

The protocol specified visits/weeks and corresponding time windows used for visit-wise analyses are presented in [Table 2](#) in terms of days relative to the date of first dose (i.e., Day 1).

**Table 2** Windowing Rules

Week	Target Visit Date (Study day)	Visit Window (Study day)
Baseline a	1	–
Week 4	28	2 – 42
Week 8	56	43 – 70
Week 12	84	71 – 98
Week 12 (LOCF) b,d	–	–
Week 16	112	99 – 126
Week 20	140	127 – 154
Week 24	168	155 – 182

**Table 2 Windowing Rules**

Week	Target Visit Date (Study day)	Visit Window (Study day)
Week 24 (LOCF) c d	—	—
End of Treatment e	—	—

- a The last non-missing values including unscheduled assessments on or prior to the date of first dose.
- b The last non-missing values including unscheduled assessments up to Day 98 (inclusive) will be carried forward as the data for the efficacy analysis, which is known as Week 12 (LOCF).
- c The last non-missing values including unscheduled assessments up to Day 182 (inclusive) will be carried forward as the data for the efficacy analysis, which is known as Week 24 (LOCF).
- d For subjects who discontinued the study, the last non-missing values up to 14 days after the date of last dose will be carried forward as the data for the efficacy analysis.
- e The last non-missing values including unscheduled assessments during the study will be used for the safety analysis only.

In case of multiple assessments within the same visit window, the assessment closest to the target visit day will be used in data analyses; in the event of two assessments being equally close to the scheduled visit day, the latest assessment in time will be used. In the event of two assessments being equally close to the scheduled visit day, the data will be considered in an individual case.

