**Table 1      Treatments Administered**

	Treatment I Phase (4 weeks)	Treatment II Phase (20 weeks)	
	Day 1 to Day 28	Day 29 to Day 84 (8 weeks)	Day 85 to Day 168 (12 weeks)
Test treatment	Dotinurad 1 mg One dotinurad 1 mg tablet and one febuxostat 20 mg-matched placebo tablet (Except Day 0)	Dotinurad 2 mg One dotinurad 2 mg tablet and two febuxostat 20 mg-matched placebo tablets	Dotinurad 4 mg Two dotinurad 2 mg tablets and two febuxostat 20 mg-matched placebo tablets
Comparator treatment	Febuxostat 20 mg One febuxostat 20 mg tablet and one dotinurad 1 mg-matched placebo tablet (Except Day 0)	Febuxostat 40 mg Two febuxostat 20 mg tablets and one dotinurad 2 mg-matched placebo tablet	Febuxostat 40 mg Two febuxostat 20 mg tablets and two dotinurad 2 mg-matched placebo tablets

The study drug will be administered orally once daily at approximately the same time each day.

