#### 4.4.2 Secondary Efficacy Analyses

For all the secondary efficacy analyses, no multiplicity adjustment will be made.

- Proportion of subjects with  $\leq 6.0$  mg/dL in SUA level at Week 12 (LOCF)

The difference in responder rate at Week 12 (LOCF) between dotinurad 2 mg and febuxostat 40 mg and the stratified 95% confidence interval will be estimated based on Mantel–Haenszel method adjusting for the baseline SUA level and baseline BMI. The prespecified non-inferiority margin will be  $-10\%$  in this analysis, which will be for the reference purpose only. The number (percentage) of responder and the asymptotic 95% confidence interval at Week 12 (LOCF) (see section 7) will be presented by treatment group.

The same analysis mentioned above will be repeated supplementally based on the PP Analysis Set.

- Proportion of subjects with  $\leq 6.0$  mg/dL in SUA level at each time point

The number (percentage) of responder at each visit (Week 4, Week 8, Week 12, Week 16, Week 20, Week 24) will be presented by treatment group.

Responder rate for each treatment group at each visit (Week 4, Week 8, Week 12, Week 12 (LOCF), Week 16, Week 20, Week 24, Week 24 (LOCF)) will be presented by bar chart.

- Mean percent reduction from baseline in SUA level at each time point

The mean percent reduction from baseline in SUA level at each visit (Week 4, Week 8, Week 12, Week 12 (LOCF), Week 16, Week 20, Week 24, Week 24 (LOCF)) will be summarized by treatment group using descriptive summary statistics. In addition, box-plot will be used for graphical presentation.

The following subgroup analysis will be repeated:

- SUA level category ( $<9$ ; 9 to  $<10$ ; 10 to  $<11$ ;  $\geq 11$  mg/dL)
- BMI category ( $<25$ ;  $\geq 25$  kg/m $^2$ )
- Classification of hyperuricemia (overproduction type, underexcretion type, combined type, other type)

In addition, the mean percent reduction and difference in least squares (LS) means between dotinurad and febuxostat, and corresponding 95% confidence interval will be estimated based

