on the mixed-effects models for repeated measures (MMRM). The model will be adjusted for the baseline SUA value, baseline SUA level category (<9; 9 to <10; 10 to <11;  $\geq 11$  mg/dL) and baseline BMI category (<25;  $\geq 25$  kg/m^2), treatment, time (Week 4, Week 8, Week 12, Week 16, Week 20, Week 24) and the interaction of treatment by time. The Kenward-Roger approximation will be used to estimate denominator degrees of freedom. The unstructured covariance matrix (UN) will be used in the analysis. In the case of nonconvergence of UN, the toeplitz covariance matrix (TOEP) will be used. In the case of nonconvergence with TOEP, the autoregressive covariance matrix [AR (1)] will be used in the model. The use of MMRM will be based on the assumption of missing at random (MAR), which means no imputation for missing values will be conducted.

- Mean SUA level and mean change from baseline in SUA level at each time point

The mean actual value and the mean change from baseline in SUA level at each time point (Baseline, Week 4, Week 8, Week 12, Week 16, Week 20, Week 24, Week 24 (LOCF)) will be summarized by treatment group using descriptive summary statistics and presented by box-plot.

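### Week 12 (LOCF) has no dose limit, so an SUA taken after the step-up to 4 mg can count in the comparison labelled dotinurad 2 mg (minor)

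*SAP*

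**What the plan says.** SAP Section 4.4.2 sets out the Week 12 comparison as "The difference in responder rate at Week 12 (LOCF) between dotinurad 2 mg and febuxostat 40 mg", estimated by the Mantel–Haenszel method with a stratified 95% confidence interval. It gives a non-inferiority margin of -10%, "which will be for the reference purpose only". Protocol Section 8.2 and SAP Section 2.1.2 nevertheless list confirming non-inferiority of 2 mg at Week 12 as a secondary objective.

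The Week 12 (LOCF) value comes from SAP Table 2, footnote b: "The last non-missing values including unscheduled assessments up to Day 98 (inclusive) will be carried forward as the data for the efficacy analysis". Footnote d adds that, for subjects who discontinued, values up to 14 days after the last dose may be used. That limits time since dosing, not dose level.

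Protocol Table 1 gives the third dosing period as "Day 85 to Day 168 (12 weeks"), with dotinurad at 4 mg and febuxostat still at 40 mg. Protocol Table 3 allows Visit 5 (Week 12) on Days 77 to 91 and Visit 6 on Days 105 to 119. SUA is sampled at early termination (Protocol 9.5.1.2.1) and, at the investigator's discretion, at unscheduled visits (Table 3, footnote o).

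**The concern.** Days 85 to 98 lie after the planned step-up but inside the reach of footnote b. Because the last value wins, a sample taken on 4 mg in that interval displaces a valid sample taken on 2 mg a few days before. The result is still reported as a 2 mg result.

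Only one arm changes dose. If 4 mg lowers SUA more than 2 mg does, samples taken on drug after the step-up shift the difference in favour of dotinurad. For early-termination samples taken off drug the direction is uncertain. What is at stake is whether the estimate offered for the 2 mg non-inferiority objective contains only values on the labelled dose.

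**Working it through.** **The plan's own figure.** With 225 per group, 45% versus 60% and two-sided alpha 0.05 (SAP Section 3), the two-group chi-square test has power 0.893 (0.897 with unpooled variance). This agrees with the stated 90% or so. Nothing below changes it.

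**Days.** Days 85 to 98 are 98 − 85 + 1 = 14 days. Scheduled visits hardly enter this interval on 4 mg:
- The Visit 5 sample, even on Days 85 to 91, normally precedes the first dose from the new pack.
- Visit 6 opens at Day 105, after Day 98.
- Under the delayed step-up for unresolved gouty arthritis (Protocol 9.4.7.4), a sample taken before the delayed pack is started is still on 2 mg.

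That leaves early-termination samples and discretionary unscheduled samples.

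**Affected share q (assumed).** The documents give neither q nor a dropout rate. As a rough guide, if dropout is even over 168 days and each subject leaving on Days 85 to 98 has an SUA on 4 mg, q = dropout × 14/168:
- 6% dropout: 0.5% (0.005 × 225 = about 1 subject)
- 12% dropout: 1% (about 2)
- 24% dropout: 2% (4 to 5)

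This is not a bound. It omits unscheduled samples and any step-up before Day 85 after an early Visit 5. It also counts subjects who never stepped up or were sampled off drug. I use 0.5% to 2% as a range.

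**Inflation of the difference.** The documents assume no response rate for 2 mg. Take febuxostat at 45% (SAP Section 3), 2 mg truly equal to it, and 60% after the step-up (the Week 24 assumption for 4 mg), which is a 15-point gain. Inflation = q × 15 points:
- q = 0.5%: 0.075 (about 0.08)
- q = 1%: 0.15
- q = 2%: 0.30

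The unstratified 95% half-width is 1.96 × √(2 × 0.45 × 0.55/225) = 0.092, or 9.2 points.

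**Chance of clearing the margin at a true difference of -10 points.** Take a true 2 mg rate of 35% and the same 15-point gain, so an apparent rate p = 0.35 + 0.15q. Then P(lower limit > -10 points) = Φ[(p − 0.45 + 0.10)/SE − 1.96], with SE = √{[p(1 − p) + 0.45 × 0.55]/225}, about 0.046:

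| q | p | P |
|---|---|---|
| 0 | 0.3500 | 2.5% |
| 0.5% | 0.35075 | 2.6% |
| 1% | 0.3515 | 2.7% |
| 2% | 0.3530 | 2.9% |

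**The case against.** The strongest reply is that this almost never happens and does not matter when it does. Visit 5 and the new pack go together, the next scheduled sample falls outside the limit, and unscheduled SUA is discretionary. Subjects stopped for unresolved gouty arthritis at Week 12 never step up. Those sampled soon after the step-up have had at most about two weeks of 4 mg, so giving them the Week 24 response rate is generous. The margin carries no formal claim, and SAP Section 7 lets the sponsor settle data handling before database lock. All of this stands and is why the point is minor. It does not close the gap: no stated rule excludes such a value, and a general power to decide later is not a rule.

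It could also be said that "the assessment closest to the target visit day will be used in data analyses" applies before the carry-forward. The SAP does not give that order. Even if it did, Visit 5 on Day 77 and an unscheduled sample on Day 86 would leave the later one in place, since |86 − 84| = 2 is less than |77 − 84| = 7. On Table 1's Day 85 start, however, that subject would have had at most two 4 mg doses.

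A reader might go further and infer that the observed Week 12 window (Days 71 to 98) also contaminates the 2 mg comparison. It does not: that comparison uses only Week 12 (LOCF). The windows are the "corresponding time windows used for visit-wise analyses" and feed the by-visit responder counts and the MMRM, which are labelled by treatment group without a dose. The SAP does not present those outputs as a check on the Week 12 (LOCF) result.

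A reader might also apply the 60% rate in the scenario with a true 2 mg rate of 35%. That is a 25-point gain and gives 2.7%, 2.8% and 3.2%, but it is a different assumption from the 15 points behind the inflation figures.

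**Conclusion.** The gap is real and minor. Footnote b can put a 4 mg value into a comparison labelled 2 mg, and neither footnote d nor the general wording of SAP Section 7 prevents it. For an assumed 0.5% to 2% of dotinurad subjects and a 15-point gain, the distortion is about 0.08 to 0.30 points, small beside a half-width of about 9.2 points, and the chance of wrongly clearing the margin rises by at most about 0.4 percentage points (2.5% to 2.9%). These sizes rest on an assumed share, an assumed gain and an unstratified normal approximation.

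The documents do not support reading this as a material bias in the Week 12 result or as any threat to the Week 24 primary analysis. It deserves correction because the mismatch is one-sided, the label is explicit and the repair is cheap.

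**What to change.** Before unblinding, amend footnote b so that Week 12 (LOCF) is the last non-missing SUA that is both up to Day 98 and sampled before the subject's first dose from the pack dispensed at the Week 12 step-up (Visit 5 or the delayed unscheduled visit). If that first-dose date is not in the database, accept samples on or before the pack's dispensing date. Apply this identically in both arms, and state that footnote d operates within the limit. Keep last value as the carry-forward rule.

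Leave the observed Week 12 window as it is. Capping it would remove usable samples from every visit window, because Week 16 opens only at Day 99, and this would include febuxostat values on an unchanged dose. A note on the by-visit and MMRM outputs that Week 12 may include a few samples taken after the step-up is enough.

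Editorial: the two sentences below Table 2 on equally close assessments conflict (latest in time, or case by case). Keep one.

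Cost: a footnote, some programming, and a few samples after the step-up, in both arms, not used for Week 12 (LOCF). Sampling date and time are already in the CRF (Protocol 9.5.1.2.1). Pack-level dates must be confirmed: Protocol 9.4.10 shows that dispensing records are kept, and SAP 4.2.6 uses tablet counts, but neither shows that the dates are in the analysis database. No visit, sample or dosing rule changes.

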#### Missing data handling

- Non-responder imputation for responder analysis of SUA (as binary variable)  
Missing values will be considered as non-responders. This handling will be applied to the sensitivity analysis of the primary efficacy analysis.
- Longitudinal data analysis of SUA using MMRM (as continuous variable)  
SUA will be analyzed using MMRM based on the assumption of missing at random (i.e., MAR). This analysis assumes subjects with missing values behave the same as the observed data within that treatment group, i.e., the missingness is independent of unobserved data after accounting for the observed data in the model.
- AE severity and AE relationship to study drug  
For the purpose of summarizing maximum severity, if the severity of an AE is missing for a subject, then, if this subject has another AE with the same preferred term that has “severe” severity, the maximum severity of the AE will be noted as “severe”; otherwise the maximum severity will be noted as missing. Similarly, for the purpose of summarizing treatment-related TEAE, if the relationship of an AE to study drug is missing, the AE will be noted to be related.
- Determination of TEMAVs for laboratory values  
For determining TEMAVs of laboratory values, a missing baseline laboratory value will be assumed to be of grade 0.

#### Handling of below lower quantification values in laboratory tests

In the cases where laboratory result contains below lower quantification (BLQ) value, it will be replaced to the lower limit value of quantification (LLOQ) for summary tables.

#### Handling of hemolysis or lipemia in laboratory specimen

If the hemolysis or lipemia occurs, those data will not be used in the analysis of laboratory test results and efficacy analysis (i.e., SUA).

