#### 4.4.1 Primary Efficacy Analyses

The analysis for the difference in the proportion of subjects with  $\leq 6.0 \text{ mg/dL}$  in SUA level (i.e., responder rate) at Week 24 (LOCF) (see section 7) between dotinurad 4 mg and febuxostat 40 mg will be conducted based on a Cochran–Mantel–Haenszel (CMH) test stratified by baseline SUA level and baseline BMI. The difference in responder rate between dotinurad 4 mg and febuxostat 40 mg and the stratified 95% confidence interval based on Mantel–Haenszel method adjusting for the baseline SUA level and baseline BMI will be estimated. Also, the number (percentage) of responder and the asymptotic 95% confidence interval will be presented by treatment group. The same primary efficacy analysis mentioned above will be repeated supplementally based on the PP Analysis Set.

For the primary efficacy endpoint, non-responder imputation method on FAS will also be implemented as a sensitivity analysis, which will handle the missing data of SUA at Week 24 as non-responder (see section 7).

The following subgroup will be investigated for the responder rate at Week 24 (LOCF):

- SUA level category ( $<9$ ;  $9 \text{ to } <10$ ;  $10 \text{ to } <11$ ;  $\geq 11 \text{ mg/dL}$ )

- BMI category ( $<25$ ;  $\geq 25$  kg/m $^2$ )
- Classification of hyperuricemia (overproduction type, underexcretion type, combined type, other type)

For the subgroup analyses, the number (percentage) of responder and the 95% confidence interval will be presented by treatment group. Furthermore, the difference in responder rate and unstratified 95% confidence interval will also be presented.

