#### 4.6.3 Laboratory Values

Laboratory results will be summarized using Système International (SI) units, as appropriate. For all quantitative parameters listed in protocol Section 9.5.1.4.4, the actual value and the change from baseline to each postbaseline visit will be summarized by visit and treatment group using descriptive statistics. Qualitative parameters listed in protocol Section 9.5.1.4.4 will be summarized using frequencies (number and percentage of subjects), and changes from baseline to each postbaseline visit will be reported using shift tables. Percentages will be based on the number of subjects with both nonmissing baseline and relevant postbaseline results.

Laboratory test results will be assigned a low/normal/high (LNH) classification according to whether the value was below (L), within (N), or above (H) the laboratory parameter's reference range. Within-treatment comparisons for each laboratory parameter will be based on 3-by-3 tables (shift tables) that compare the baseline LNH classification to the LNH classification at each postbaseline visit. Similar shift tables will also compare the baseline LNH classification to the LNH classification for the highest and lowest value.

[Appendix 1](#) (Sponsor's Grading for Laboratory Values) presents the criteria that will be used to identify subjects with treatment-emergent markedly abnormal laboratory values (TEMAVs). A TEMA V is defined as a postbaseline value with an increase from baseline to a grade of 2 or higher. When displaying the incidence of TEMA Vs, each subject may be counted once in the laboratory parameter high and in the laboratory parameter low categories, as applicable.

The number (percentage) of subjects with TEMA V (markedly abnormal high/low) will be summarized by treatment group.

The number (percentage) of subjects who met the following criteria for the hepatic test at the same time will be summarized by treatment group. If a subject met the criteria more than once for available laboratory data, the subject will be counted only once in the calculation of the incidence.

- Elevated AST or ALT lab value that is greater than or equal to  $3 \times$  ULN
- Elevated total bilirubin lab value that is greater than or equal to  $2 \times$  ULN
- Alkaline phosphatase lab value that is less than  $2 \times$  ULN

A subject data listing of laboratory values will be provided.

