Bilirubin (hyperbilirubinemia)	>ULN – 1.5×ULN if baseline was normal; 1.0 – 1.5×baseline if baseline was abnormal	>1.5 – 3.0×ULN if baseline was normal; >1.5 – 3.0×baseline if baseline was abnormal	>3.0 – 10.0×ULN if baseline was normal; >3.0 – 10.0×baseline if baseline was abnormal	>10.0×ULN if baseline was normal; >10.0×baseline if baseline was abnormal
Calcium, serum-low (hypocalcemia)	<LLN – 8.0 mg/dL <LLN – 2.0 mmol/L Ionized calcium <LLN – 1.0 mmol/L	<8.0 – 7.0 mg/dL <2.0 – 1.75 mmol/L Ionized calcium <1.0 – 0.9 mmol/L	<7.0 – 6.0 mg/dL <1.75 – 1.5 mmol/L Ionized calcium <0.9 – 0.8 mmol/L	<6.0 mg/dL <1.5 mmol/L Ionized calcium <0.8 mmol/L
Calcium, serum-high (hypercalcemia)	>ULN – 11.5 mg/dL >ULN – 2.9 mmol/L Ionized calcium >ULN – 1.5 mmol/L	>11.5 – 12.5 mg/dL >2.9 – 3.1 mmol/L Ionized calcium >1.5 – 1.6 mmol/L	>12.5 – 13.5 mg/dL >3.1 – 3.4 mmol/L Ionized calcium >1.6 – 1.8 mmol/L	>13.5 mg/dL >3.4 mmol/L Ionized calcium >1.8 mmol/L
Creatinine	>ULN – 1.5×ULN	>1.5 – 3.0×baseline; >1.5 – 3.0×ULN	>3.0×baseline; >3.0 – 6.0×ULN	>6.0×ULN

	Grade 1	Grade 2	Grade 3	Grade 4
GGT ( $\gamma$ -glutamyl transpeptidase)	>ULN – 2.5 $\times$ ULN if baseline was normal; 2.0 - 2.5 $\times$ baseline if baseline was abnormal	>2.5 – 5.0 $\times$ ULN if baseline was normal; >2.5 - 5.0 $\times$ baseline if baseline was abnormal	>5.0 – 20.0 $\times$ ULN if baseline was normal; >5.0 - 20.0 $\times$ baseline if baseline was abnormal	>20.0 $\times$ ULN if baseline was normal; >20.0 $\times$ baseline if baseline was abnormal
Glucose, serum-low (hypoglycemia)	<LLN – 55 mg/dL <LLN – 3.0 mmol/L	<55 – 40 mg/dL <3.0 – 2.2 mmol/L	<40 – 30 mg/dL <2.2 – 1.7 mmol/L	<30 mg/dL <1.7 mmol/L
Potassium, serum-high (hyperkalemia)	>ULN – 5.5 mmol/L	>5.5 – 6.0 mmol/L	>6.0 – 7.0 mmol/L	>7.0 mmol/L
Potassium, serum-low (hypokalemia)	<LLN – 3.0 mmol/L		<3.0 – 2.5 mmol/L	<2.5 mmol/L
Sodium, serum-high (hypernatremia)	>ULN – 150 mmol/L	>150 – 155 mmol/L	>155 – 160 mmol/L	>160 mmol/L
Sodium, serum-low (hyponatremia)	<LLN – 130 mmol/L	125-129 mmol/L	120-124 mmol/L	<120 mmol/L

	Grade 1	Grade 2	Grade 3	Grade 4
Triglyceride, serum-high (hypertriglyceridemia)	150 – 300 mg/dL 1.71 – 3.42 mmol/L	>300 – 500 mg/dL >3.42 – 5.7 mmol/L	>500 – 1000 mg/dL >5.7 – 11.4 mmol/L	>1000 mg/dL >11.4 mmol/L

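### The SAP's hemolysis and lipemia exclusion is not limited to analytes the laboratory finds invalid, so it can remove high triglyceride values from the tables meant to count them

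*SAP*

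**What the plan says.** The rule is one sentence in SAP section 7, under the heading on hemolysis or lipemia: "If the hemolysis or lipemia occurs, those data will not be used in the analysis of laboratory test results and efficacy analysis (i.e., SUA". Nothing there refers to the analyte, the degree of interference, the laboratory's own validity judgement, a repeat draw, or an analysis with the values kept.

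It feeds into these analyses:

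- **By-visit summaries (SAP 4.6.3).** For the quantitative parameters, "the actual value and the change from baseline to each postbaseline visit will be summarized by visit and treatment group using descriptive statistics".
- **Extreme-value shift tables (SAP 4.6.3).** "Similar shift tables will also compare the baseline LNH classification to the LNH classification for the highest and lowest value".
- **TEMAVs (SAP 4.6.3).** A TEMAV "is defined as a postbaseline value with an increase from baseline to a grade of 2 or higher". The graded parameters in SAP Appendix 1 include "Triglyceride, serum-high (hypertriglyceridemia"): grade 2 is above 300 to 500 mg/dL, grade 3 above 500 to 1000, and grade 4 above 1000.
- **Combined hepatic criterion (SAP 4.6.3).** "The number (percentage) of subjects who met the following criteria for the hepatic test at the same time will be summarized by treatment group".
- **Missing baseline (SAP section 7).** For TEMAVs, "a missing baseline laboratory value will be assumed to be of grade 0".
- **SUA.** The primary endpoint uses LOCF up to Day 182 (SAP Table 2, footnote c). The sensitivity analysis in SAP 4.4.1 is non-responder imputation (NRI), "which will handle the missing data of SUA at Week 24 as non-responder".

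The protocol's laboratory analysis section (9.7.1.8.3) has no such exclusion. Its only related text is in 9.5.1.1.3, on classifying hyperuricemia. There, hemolysed or chylous samples matter only when the laboratory or the investigator regards a parameter as reference or unmeasurable data.

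**The concern.** Dropping a result that interference has made invalid is good practice. This rule acts on the appearance of the specimen and does not ask whether a given result is invalid.

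For most analytes that costs some data. For triglycerides it is a different kind of problem. Lipemia is excess lipid in the specimen, so whether a value is excluded depends on the value. A table that counts high triglycerides after removing lipemic specimens is censored on its own outcome.

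Three further consequences follow. A flagged baseline can produce a false emergent case. Liver and renal results from the same draw can drop out of the by-arm laboratory tables. A measured Week 24 SUA can be treated as missing.

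**Working it through.** The documents give no frequency of hemolysis or lipemia and no flagging threshold, so the plan has no figure on this point to reproduce. Every rate below is an assumption shown as a range.

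**1. Triglycerides.** They are collected (protocol Table 2) and graded (SAP Appendix 1). No exclusion criterion in protocol 9.3.2 concerns triglycerides, and stable lipid-lowering drugs are allowed (9.4.7.2), so patients with high values can be enrolled. Let *I* be the true share of subjects with a triglyceride TEMAV, and *s* the share of those who qualify only on lipemic specimens. The table then shows *I*(1 − *s*), and 225 × *I* × *s* subjects per arm are lost.

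- *I* = 20%: *s* = 10%, 25%, 50% gives a displayed rate of 18%, 15%, 10%, with about 5, 11, 23 subjects lost.
- Low end: 225 × 0.10 × 0.10 = 2.25 subjects.
- High end: 225 × 0.30 × 0.50 = 33.75 subjects.

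The loss of grade 3 and 4 values depends on where flagging starts. Assume a lognormal distribution with median 150 to 200 mg/dL and log-scale SD 0.5 to 0.7. Flagging above 500 mg/dL then removes all grade 3 or higher values, above 800 removes 5% to 25% of them, and above 1000 removes 1% to 11%.

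**2. Baseline.** Protocol Table 3 schedules one laboratory panel before dosing, at screening. Take a baseline of 600 mg/dL (grade 3) and a later value of 320 mg/dL (grade 2).

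- Baseline kept: grade 3 to grade 2, no increase, not a TEMAV.
- Baseline excluded with no other pre-dose value: grade 0 by rule, then grade 2, counted as a TEMAV.

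The same table can therefore miss real events and add false ones.

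**3. Liver and renal analytes.** ALT, AST, bilirubin and creatinine are lost when they come from a flagged specimen. For a rare finding, one lost case changes an arm from 1/225 = 0.44% (exact 95% CI 0.01 to 2.45) to 0/225 (0 to 1.63).

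**4. SUA.** The NRI illustration starts from the design rates, so I checked those first. Power = Φ{[|p₁ − p₂|√n − 1.96√(2p̄(1 − p̄))] / √(p₁(1 − p₁) + p₂(1 − p₂))}. With n = 225, p₁ = 0.45, p₂ = 0.60 and p̄ = 0.525, this is Φ{(2.25 − 1.384)/0.698} = 0.893, which agrees with the stated 90% or so.

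Now assume a share *f* of Week 24 specimens is flagged equally in both arms, independent of response, with no other value in Days 155 to 182. NRI multiplies each rate by 1 − *f*:

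- *f* = 5% (22.5 of 450 subjects): 57.0% vs 42.75%, difference 14.25 points, power 0.859.
- *f* = 10% (45 of 450): 54.0% vs 40.5%, difference 13.5 points.

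Under LOCF the flagged value gives way to an earlier one. Weeks 16 and 20 fall in the same dose period as Week 24 (Days 85 to 168), so a carried-forward value would usually come from the same dose. The documents give no basis for sizing this effect.

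**The case against.** **The wording may be meant more narrowly.** The phrase for what is dropped could mean only the affected analytes. SAP section 8 places derivation rules in separate documents, and section 7 lets the sponsor settle data handling before database lock. This stands as a reason to clarify. It does not remove the problem, because the SAP does not state the narrower meaning and a programmer could apply the rule to the whole specimen. Even an affected-analytes reading might drop triglycerides for lipemia.

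**Liver and renal cases stay visible.** A reader might infer that the rule hides liver or renal signals from the safety report. The documents do not support that:

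- Liver injury and acute renal failure are always reported as adverse events (protocol 9.5.1.4.3) and are tabulated by arm (SAP 4.6.2).
- The hepatic combination goes on the Adverse Event CRF whether serious or not, with at least weekly retesting (protocol 9.5.4.3.2).
- A laboratory listing is provided (SAP 4.6.3).
- One unflagged repeat specimen that still meets the criteria puts the subject back in the hepatic or TEMAV table.

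**The flag rate may be low.** Subjects attend without the preceding meal (protocol 9.4.9), which argues against frequent meal-related lipemia. Unscheduled SUA measurements are possible (protocol Table 3, footnote o), and baseline may use any pre-dose value, including unscheduled ones. All of this stands. It limits how often the problem arises, and it also makes high fasting triglycerides a more likely cause of the lipemia that remains.

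**NRI is doing its job.** Counting missing as failure is what the method is defined to do. The shift is small, sits in a sensitivity analysis, and under equal flagging works against the superiority claim. That is fair. The remaining point is that a valid measured value need not have been made missing.

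**Conclusion.** The concern holds for the laboratory tables. As written, the SAP excludes data from hemolysed or lipemic specimens with no limit by analyte and no role for the laboratory's judgement. For triglycerides this removes values from the upper tail that the TEMAV and highest-value tables exist to count. With one scheduled pre-dose panel, the grade 0 rule can also create false emergent cases.

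The size cannot be derived from the documents. Under the assumed ranges, between about 2 and 34 subjects per arm could be missing from the triglyceride TEMAV count. It would be tempting to say that most grade 3 and 4 triglyceride events vanish. That depends entirely on an unstated flagging threshold, and the illustration runs from 1% of grade 3 or higher values to all of them.

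For ALT, AST, bilirubin and creatinine, the finding is possible absence from the by-arm laboratory tables only. For SUA, it is an avoidable loss of valid values. The documents do not show a material effect on the primary test.

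**What to change.** Replace the sentence in SAP section 7 with a rule at analyte level:

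1. Exclude a result only when the central laboratory reports that analyte, including uric acid, as invalid for that specimen.
2. Do not exclude triglycerides because of lipemia alone.
3. Where a reported but flagged baseline value exists, use its grade for TEMAVs. Keep grade 0 for subjects with no reported baseline.
4. Tabulate excluded results by arm and analyte.
5. Repeat the TEMAV, hepatic and SUA analyses with all reported values kept, whatever their level.

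Flagged values should not be kept only when they cross a stopping or reporting threshold. That would select on the outcome and inflate the abnormal rates.

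The cost is one SAP paragraph, one count table and a repeat run of existing programs, all before unblinding. It needs a validity report by analyte from the central laboratory. The documents do not say whether one is supplied, so this should be confirmed. The downside is that a few values with minor interference stay in the tables.
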